1. PURPOSE OF THE STUDY

a. Brief Summary

The purpose of the research is to assess the effectiveness of a medication called tranexamic acid (TXA) when given intraoperatively to reduce bleeding postoperatively after sinonasal surgery (e.g. septoplasty, endoscopic sinus surgery). This medication has already been shown to decrease blood loss during surgery, but the implications for bleeding after surgery are unclear. Any impact on postoperative bleeding from the nose will be assessed over the first 7 days following surgery leading up to the first postoperative clinic visit.

b. Objectives

We hope to learn whether use of the tranexamic acid (TXA) lowers the amount of bleeding after surgery as well as the need for repeat evaluation and additional intervention including nasal packing, cautery, and return trips to the OR. If the medication proves effective in doing so, this knowledge will help provide a rationale for sinus surgeons to routinely use this medication intraoperatively to reduce postoperative bleeding, thereby improving the patient experience and reducing use of hospital resources, both in terms of physical and human capital.

c. Rationale for Research in Humans

This study evaluates the clinical effect of tranexamic acid (TXA) on bleeding followed sinonasal surgery. As a clinical study, it necessarily involves the use of human subjects to assess the impact. The study will also evaluate the patient experience and the impression that patients have of their own bleeding following these procedures.

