study in a clinical context if they meet the screening requirements. Screening may occur either at the preoperative visit that is part of the standard of care, or on the morning of surgery during the surgical consent process if the patient decided to schedule surgery remotely without a preoperative visit. For any patients who have their pre-op visit via telehealth instead of in-person, it will still be brought up in the clinical context of that pre-operative visit. If a patient is interested, the patient will receive more information regarding the study details, and if the patient wishes to participate after a full informed consent process, written consent will be obtained. Patients will need to be able to provide voluntary consent; those who cannot will be excluded. Patients will be excluded if they are under 18 years of age, are pregnant or may become pregnant by time of surgery, are prisoners, are international participants, are unable to provide consent, or are non-English speaking. Patients will also be excluded if they have known pro-thrombotic clotting disorders. Other patients that are not specifically targeted but will not necessarily be excluded include employees and students, as long as they are able to provide voluntary consent. Once a patient has had all questions answered and has voluntarily enrolled in the study, the patient will be provided with a bleeding diary template to record the postoperative experience which include VAS evaluation postoperative bleeding and number of gauze changes per day. They will use this diary template daily postoperatively. Patients will be randomized to receive either the study medication (TXA with saline infusion) or not (saline infusion alone). The surgeon will be blinded to this selection. The anesthesiologist will not be blinded. However, the patient's participation in the study will be announced during the surgical time out, and it will be announced that the attending surgeon is blinded to the patient's participation. The patient will undergo general anesthesia and undergo their sinonasal surgery as routine. The study intervention will occur 15 minutes before completion of the surgery. At this time, a 1,000 mg IV dose of tranexamic acid will be added to the saline infusion by the anesthesiologist for patients randomized to the intervention. Patients randomized to placebo will continue to receive their routine infusion of normal saline, which is administered throughout surgery. The anesthesiologist will be asked only to state 'study medication administered' at the time of administration, whether the infusion consists of saline alone or with the addition of TXA. This will be the only way in which the two study arms differ. To standardize patient management, packing materials (e.g. nasopore, surgical, Floseal) will not be used at the end of a surgery. However, if a patient experiencing clinically concerning bleeding at the termination of surgery that requires use of these materials (or the clinically indicated use of a dose of TXA), they will be unblinded, removed from the protocol, and managed accordingly. Patient safety will always take priority. After reversal of anesthesia and extubation, patients will be transported to recovery as per standard of care. They will be discharged home when meeting routine post-anesthesia criteria (tolerating oral intake, control of nausea, control of pain, etc). After discharge home and through the following week leading up to their postoperative visit, all patients will fill out the diary template outlined above to characterize their daily postoperative bleeding. Patients will then follow up for their first postoperative clinic visit one week after surgery which is the standard of care. They will turn in their postoperative bleeding diary entries at this time. Their active obligation at this point is over, but they will always have the right to have their data removed from analysis if they wish to withdraw. They will not be contacted for research purposes after this point in regards to this specific study, but will continue to follow up clinically as per standard of care. They will have no clinic visits exclusively for

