
research purposes; the only visits will be part of the standard of care. Surgical residents will maintain a list of study patients on whom they are called to evaluate for postoperative bleeding in the recovery unit. They will be blinded to whether the patient received the study medication or placebo. Records (i.e. via STARR) will be queried to determine the frequency with which patients in each group call the clinic or answering service with bleeding- related concerns. Records of further intervention (nasal packing, cautery, return to OR) will also be gathered. These outcomes will be used to determine the difference between groups. Patients will have received the standard of care for postoperative epistaxis in all these scenarios, identical to patients who are not enrolled in the study. The primary outcome is the patient-reported VAS bleeding score after surgery. This methodology has been used by other published work to assess the impact of agents used at the end of procedures to reduce the rate of postoperative bleeding after sinonal surgery (<https://journals.sagepub.com/doi/10.1016/j.otohns.2009.06.078>). Using their results as a reference, we may expect that the VAS score on postoperative day one may drop from a 4 to a 2. Assuming an SD of 1.6-1.8 for the purpose of estimations, we would need 24-28 total cases to detect the effect size of 2 in VAS if using 1:1 ratio with 80% power. The secondary outcome is the frequency with which the service is requested to evaluate patients in the recovery unit for postoperative bleeding concerns after sinonal surgeries. Anecdotal feedback from the resident service suggests that they are requested to evaluate roughly 30% of these patients. With the hypothesis that the TXA could reduce the frequency by roughly half to 15%, we will require 118 patients in each group (total N=236) to achieve 80% power to detect a difference between the two group proportions of 15% (with 30% in placebo, 15% in TXA group). This estimate uses two sided Z-test while assuming type I error=0.05.

b. Procedure Risks

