Patients data will be gathered for one week postoperatively and their direct participation will end at the first clinical visit one week after surgery (their data will still be analyzed after that time). The primary endpoint is the patient VAS assessment of postoperative bleeding over the first week, and the patient report of gauze usage over the first week. Secondary endpoints to be evaluated will include the proportion of patient in recovery on whom the nurses contact the on-call resident for assessment with postoperative bleeding, the need for interventions to address postoperative bleeding (cautery, nasal packing, return to OR), and frequency of patient calls to clinic after discharge home with bleeding concerns. If during interim data analysis a significant difference in postoperative bleeding is noted without an increase in adverse events, discussion could be had with the IRB over developing a new standard of care, however we would anticipate continuing with the standard of care through the end of the study.

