7. DISINFECTION PROCEDURES FOR MEDICAL EQUIPMENT USED ON BOTH HUMANS AND ANIMALS

N/A

8. PARTICIPANT POPULATION**a. Planned Enrollment**

All patients will be recruited at Stanford Sinus Center. Given the expected number of patients to power the study based on the calculations listed in section 2a, this will include approximately 250 total patients. To be included, patients will have to be scheduled for sinonasal surgery, as this is the population of interest. While students and employees will not be specifically targeted, they also will not be specifically excluded. Patients with surgery for sinonasal cancer will be excluded as this study will focus on routine sinonasal surgery for nasal obstruction and/or chronic rhinosinusitis.

b. Age, Gender, and Ethnic Background

Patients will include both men and women 18 years of age or older from all ethnicities that present to Stanford outpatient clinics.

c. Vulnerable Populations

Children, pregnant women, homeless, and decisional impaired patients will be excluded from the study. Students, employees, and economically and educationally disadvantaged patients will be offered the opportunity to participate in the study, however it will be made clear that if they choose not to participate they will otherwise still receive the identical standard of care. There will be no pressure to participate given the high volume of patients that are scheduled for surgery through the sinus center.

d. Rationale for Exclusion of Certain Populations

This study will only be implemented at the adult hospital. Children do not receive surgical care at the adult hospital, but rather only at LPCH. As such, by necessity, they will be excluded.

e. Stanford Populations

Laboratory personnel, employees, and students are eligible for the study, but will not be specifically targeted. All those who have been scheduled for sinonasal surgery who do not meet the exclusion criteria (pregnant women, children, prisoners, international, etc) will be offered participation in the study. No participants will receive compensation.

f. Healthy Volunteers

N/A - all patients will have a diagnosis code requiring sinus or nasal surgery

g. Recruitment Details

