iv. Specific triggers or stopping rules

The study will end when recruitment targets are reached or if interim data analysis demonstrates a statistically significant difference in endpoints between groups. If Suspected Unexpected Serious Adverse Reactions or Unanticipated Problems (UPs) are encountered, the study will be halted and possibly terminated early if the issue cannot be resolved.

v. DSMB Reporting

The outcome of the review will be disseminated to the co-investigators and the IRB.

vi. Will the Protocol Director be the only monitoring entity? (Y/N)

Yes

vii. Will a board, committee, or safety monitor be responsible for study monitoring? (Y/N)

No

f. Risks to Special Populations

N/A

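### Sections 2.a and 2.g give different primary endpoints, and the two-part first-week version has no weekly summary, no success rule and no sample size

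*Combined protocol and SAP*

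**What the plan says.** - Section 2.a (Procedures) names one measure: "The primary outcome is the patient-reported VAS bleeding score after surgery". It attaches no day or window to it.
- The sizing in the same section rests on one day: "we may expect that the VAS score on postoperative day one may drop from a 4 to a 2". With an SD of 1.6-1.8, 1:1 allocation and 80% power, it concludes "we would need 24-28 total cases to detect the effect size of 2 in VAS".
- Section 2.g (Study Endpoint(s)) names two measures: "The primary endpoint is the patient VAS assessment of postoperative bleeding over the first week, and the patient report of gauze usage", each over the first week.
- The diary in section 2.a is filled in daily and collects "VAS evaluation postoperative bleeding and number of gauze changes per day".
- Section 1.a says that any effect on bleeding "will be assessed over the first 7 days following surgery".
- Section 8.a sets enrolment: "this will include approximately 250 total patients". This follows the recovery-unit outcome in section 2.a (118 per group, 236 in total), which is secondary.
- Section 9.e.iv allows the study to end "if interim data analysis demonstrates a statistically significant difference in endpoints between groups", without naming an endpoint.

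**The concern.** The two statements of the primary endpoint differ on whether gauze use is primary. The VAS sizing also applies to one day, whereas section 2.g applies to a week.

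Three things needed to run the primary analysis are absent:

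- **A weekly summary.** Up to seven daily VAS scores and gauze counts could become a mean, a sum, a peak or a repeated-measures contrast.
- **A success rule.** The trial could succeed on VAS alone, on either measure, or only on both.
- **Planning values.** No effect or SD is given for first-week VAS or for gauze use.

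Someone must therefore choose later. Sections 8.m and 9.e have outcome data analysed every three months, with the Protocol Director as the only monitoring entity, so that choice could be made after differences between arms have been seen. An either-measure rule would also raise the false-positive rate above 5%. A both-measures rule would not, but it would lower power and rest on a measure that was never sized.

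**Working it through.** **1. Reproducing the plan's figure.** Inputs from section 2.a: difference 4 − 2 = 2, SD 1.6-1.8, 1:1 allocation, 80% power. Two-sided alpha of 0.05 is stated there only for the secondary outcome and is assumed to apply here too. Two-sample t-test:

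| SD | Standardised effect | n per arm | Total | Power at that n |
|---|---|---|---|---|
| 1.6 | 2/1.6 = 1.25 | 11.1, so 12 | 24 | 83.3% |
| 1.8 | 2/1.8 = 1.11 | 13.7, so 14 | 28 | 80.8% |

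The 24-28 is correct for a difference of 2 on one day. At 118 per arm the same difference has over 99.9% power.

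**2. Either measure suffices, each at 0.05.** Familywise error = 1 − P(|Z1| < 1.96 and |Z2| < 1.96), with Z1 and Z2 bivariate normal. The VAS-gauze correlation is not in the plan and is assumed:

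| Correlation | Familywise error |
|---|---|
| 0.3 | 9.5% |
| 0.5 | 9.1% |
| 0.7 | 8.3% |

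**3. Both measures required.** False success is at most 5%. If each measure has exactly 80% power, joint power is 66.6% at correlation 0.3 and 71.3% at 0.7.

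**4. First-week VAS as the mean of seven daily scores.** Assumed: the SD of 1.6-1.8 holds on every day, and any two days correlate at rho = 0.3-0.7.

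SD of the weekly mean = SD × √((1 + 6·rho)/7)

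- Lowest: 1.6 × √(2.8/7) = 1.01
- Highest: 1.8 × √(5.2/7) = 1.55

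At 118 per arm, 80% power needs a weekly mean difference of 0.37 (SD 1.01) to 0.57 (SD 1.55).

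Two illustrative patterns, each starting from the plan's day 1 effect of 2:

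- **Halves daily:** (2 + 1 + 0.5 + 0.25 + 0.125 + 0.0625 + 0.03125)/7 = 3.97/7 = 0.57.
- **Day 1 only:** 2/7 = 0.29.

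| Pattern | Weekly difference | Power at 118 per arm | Power at 125 per arm |
|---|---|---|---|
| Halves daily | 0.57 | 80-99% | 82-99% |
| Day 1 only | 0.29 | 29-58% | 31-60% |

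For the halving pattern, 80% power needs 102 patients in total (SD 1.6, rho 0.3) to 238 (SD 1.8, rho 0.7), not 24-28.

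**5. Gauze use.** No effect, SD or distribution is given, so its power cannot be computed at any sample size.

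**The case against.** The strongest reply has four parts.

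- **Timing.** Section 2.a attaches no day to the primary VAS; day 1 appears only in the sizing assumption. Sections 1.a and 2.g both point to the first week. This stands: on timing, 2.a is silent and does not contradict 2.g. The direct contradiction is over gauze use. The sizing still does not match a first-week endpoint.
- **Sample size.** The trial plans about 250 patients, not 24-28, and VAS keeps at least about 80% power at 118 per arm even if the effect halves daily. This stands for VAS and limits the harm. It does not settle which measure, summary or success rule applies, and it gives no assurance about gauze use.
- **Assumed inputs.** The correlations, constant SD and decay patterns are not in the plan, and the familywise figure counts differences in both directions. The 67-71% joint power also assumes exactly 80% for each measure; if VAS power is near 100%, joint power is close to that of gauze alone. These figures are therefore illustrations. The missing definitions do not depend on them.
- **Choice of remedy.** Keeping both measures as primary under a stated rule would also be coherent, and choosing day 1 moves away from the week named in 1.a and 2.g. Both points are fair. However, the two-measure route needs planning values for gauze that the plan does not have.

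**Conclusion.** The concern holds and should be corrected before the primary analysis. Section 2.a makes VAS alone primary, while section 2.g makes first-week VAS and first-week gauze use primary. No weekly summary or success rule exists, and the stated 24-28 patients at 80% power do not apply to the endpoint in 2.g.

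The documents alone establish this. Its size depends on assumptions the plan does not supply: excess error of about 3 to 4.5 percentage points under an unadjusted either-measure rule, or reduced joint power under a both-measures rule. For VAS itself the loss of power is limited by the planned enrolment. Of the two patterns computed, only an effect confined to day 1 leaves a weekly mean clearly underpowered.

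**What to change.** State the same single primary endpoint in sections 2.a and 2.g, test it at the full two-sided 0.05, and list gauze use as secondary. Two versions would work:

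1. **VAS on postoperative day 1.** This matches the existing sizing. First-week VAS becomes secondary.
2. **First-week VAS.** Define one summary, for example the mean of the seven daily scores, and rewrite the VAS sizing paragraph for that summary against the planned enrolment of about 250.

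Fix the choice before anyone sees outcome data by arm. The endpoint reference in section 9.e.iv can then point to the named endpoint; how repeated interim testing is controlled is a separate matter that this change does not resolve.

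The cost is wording in two sections, plus a rewritten sizing paragraph under the second version. No new data are needed, because the diary already collects daily VAS and gauze counts. Gauze use loses its primary status.

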3. BACKGROUND

a. Past Experimental and/or Clinical Findings

The rationale for this study is based on the findings from other groups that have consistently demonstrated a reduction in intraoperative bleeding with the use of tranexamic acid (TXA) without any significant adverse events. A systematic review and meta-analysis of 5 RCTs including 192 patients receiving a variety of routes of administration TXA (including IV, oral, and topical) demonstrated a mean decrease in operative blood loss and resulting improved surgical field quality without any difference in adverse events.(1) A more recent meta-analysis came to the same conclusions by evaluating 11 RCTs.(2) A study examining only IV TXA given at induction of anesthesia demonstrated a significant reduction in bleeding with no incidence of thrombosis in either group, one of the main theoretic concerns of TXA. (3) One patient in the study required intervention for epistaxis, and this patient was in the placebo group. A recent publication in the Laryngoscope evaluated 7 RCTs with a total of 562 patients and found reduced blood loss with TXA versus placebo with no difference in hemodynamics, coagulation profiles, emesis, or thrombotic events.(4) Numerous additional studies have proven the benefit of topical and IV TXA used intraoperatively to reduce intraoperative blood loss, with a recent randomized clinical trial demonstrating no increase in MAP, HR, PT, or PTT. (5) Given the robustness of these findings but without clear evidence to date on postoperative bleeding, nor the resource utilization spent on evaluation by the surgical

service in the recovery unit, a Cochrane protocol was developed in 2017. (6) Among the secondary outcomes of the protocol includes complications and postoperative bleeding, however the protocol has not been published and no studies since that time have answered this particular question.

4. RADIOISOTOPES OR RADIATION MACHINES

N/A

5. DEVICES USED IN THE STUDY

N/A

6. DRUGS, BIOLOGICS, REAGENTS, OR CHEMICALS USED IN THE STUDY

a. Investigational Drugs, Biologics, Reagents, or Chemicals

N/A

b. Commercial Drugs, Biologics, Reagents, or Chemicals

Commercial Product 1	
Name:	Tranexamic acid
Dosage:	1000 mg

7. DISINFECTION PROCEDURES FOR MEDICAL EQUIPMENT USED ON BOTH HUMANS AND ANIMALS

N/A

8. PARTICIPANT POPULATION**a. Planned Enrollment**

All patients will be recruited at Stanford Sinus Center. Given the expected number of patients to power the study based on the calculations listed in section 2a, this will include approximately 250 total patients. To be included, patients will have to be scheduled for sinonasal surgery, as this is the population of interest. While students and employees will not be specifically targeted, they also will not be specifically excluded. Patients with surgery for sinonasal cancer will be excluded as this study will focus on routine sinonasal surgery for nasal obstruction and/or chronic rhinosinusitis.

b. Age, Gender, and Ethnic Background

Patients will include both men and women 18 years of age or older from all ethnicities that present to Stanford outpatient clinics.

c. Vulnerable Populations

Children, pregnant women, homeless, and decisional impaired patients will be excluded from the study. Students, employees, and economically and educationally disadvantaged patients will be offered the opportunity to participate in the study, however it will be made clear that if they choose not to participate they will otherwise still receive the identical standard of care. There will be no pressure to participate given the high volume of patients that are scheduled for surgery through the sinus center.

d. Rationale for Exclusion of Certain Populations

This study will only be implemented at the adult hospital. Children do not receive surgical care at the adult hospital, but rather only at LPCH. As such, by necessity, they will be excluded.

e. Stanford Populations

Laboratory personnel, employees, and students are eligible for the study, but will not be specifically targeted. All those who have been scheduled for sinonasal surgery who do not meet the exclusion criteria (pregnant women, children, prisoners, international, etc) will be offered participation in the study. No participants will receive compensation.

f. Healthy Volunteers

N/A - all patients will have a diagnosis code requiring sinus or nasal surgery

g. Recruitment Details

Patients seen in the outpatient clinic and offered to schedule elective sinus or nasal surgery will automatically be screened for inclusion into the study. Advertisements will not be used; rather the clinician will inform the patient of the research trial and if the patient expresses interest a member of the research team will discuss the details of the trial with the patient, answer further questions, and obtain consent.

h. Eligibility Criteria

i. Inclusion Criteria

Scheduled to undergo elective sinus or nasal surgery (e.g. septoplasty, inferior turbinate reduction, endoscopic sinus surgery)
Age 18 or greater
English-speaking
Able to provide consent

ii. Exclusion Criteria

Minors (age<18)
Pregnant or may become pregnant by time of surgery
Prisoners
Non-English speaking
Foreign citizens
Unable to provide consent
Known pro-thrombotic coagulation disorders
Active intranasal drug use (e.g. cocaine)
Surgery is for a sinonasal tumor or other sinus pathology not described in inclusion criteria
Enrollment is in conflict with existing study participation

i. Screening Procedures

Patients will be screened in the outpatient clinic for inclusion in the study once electing to schedule sinonasal surgery. Their past medical history will be obtained at this time to determine eligibility. If the patient is pregnant or has a reported history of a pro-thrombotic coagulopathy, they will be excluded from the study. Medication history will also be evaluated to determine whether a patient is on blood thinners to provide context to outcomes for subset analysis. Standard of care will be used in regards to medication management before and after surgery; there will be no alteration in medication management as a result of inclusion in the study.

j. Participation in Multiple Protocols

The patient may potentially be enrolled in other unrelated study protocols. They will be asked about participation in other studies at the time of enrollment in this study to confirm there is no conflict by enrolling in this study.

k. Payments to Participants

N/A

l. Costs to Participants

Only the costs of routine medical care associated with the surgery and postoperative care will be charged to the patient, as is routine. There will be no additional costs to the patient by participating in this study.

m. Planned Duration of the Study

Once enrollment begins, the expected duration of the study is expected to be 6-12 months depending on speed of enrollment. Screening will take roughly 10 minutes during the preoperative clinic visit. Active participation in the study will last from the day of surgery to the first scheduled clinical visit one week later. Analysis of patient data will be performed quarterly.

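### Blood-thinner use and scheduled procedure are knowable before randomisation, but neither adjustment nor stratification is specified, so a small, nearly free gain in precision is not secured

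*Combined protocol and SAP*

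**What the plan says.** **Blood thinners.** Users are not excluded. Section 8.i evaluates medication history at screening to establish "whether a patient is on blood thinners to provide context to outcomes for subset analysis". It adds that "there will be no alteration in medication management as a result of inclusion in the study". No other use of the variable is stated.

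**Procedure type.** Section 8.h.i admits a mix of operations: "Scheduled to undergo elective sinus or nasal surgery (e.g. septoplasty, inferior turbinate reduction, endoscopic sinus surgery". The scheduled procedure is therefore known at enrolment. No section lists it as a study data item or gives it a role in the analysis, not even a subset.

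**Allocation.** Section 2.a says only "Patients will be randomized to receive either the study medication (TXA with saline infusion) or not (saline infusion alone". Stratification, blocking and minimisation are not mentioned.

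**Analysis.** Section 2.a states "The primary outcome is the patient-reported VAS bleeding score after surgery", and Section 2.g adds gauze use. No analysis model is given for any endpoint. The one test named closes the sample-size paragraph for recovery-unit evaluation: "This estimate uses two sided Z-test while assuming type I error=0.05".

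**The concern.** Both factors plausibly affect bleeding after surgery, and the protocol itself treats blood-thinner status as relevant to outcome. If neither the randomisation nor a prespecified model uses them, two things are left to chance. Prognostic variation stays in the error term, and an uneven split of operations or of blood-thinner users can move the treatment estimate in the one trial that is run. Adjustment would address both without extra patients.

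The one use that is stated, a subset, is the least informative. A small group of users analysed alone says little about whether the effect differs in them, and a null or extreme result there is easily misread. Because no model is written down, covariates could also be chosen after the data have been seen.

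**Working it through.** **1. The plan's own figures.**
- Recovery-unit evaluation, 30% v 15%, two-sided 0.05, 80% power, unpooled variance: n = (0.30×0.70 + 0.15×0.85)(1.960 + 0.842)² / 0.15² = 0.3375 × 7.849 / 0.0225 = 117.7, so 118 per group. This matches.
- VAS: the plan says "we may expect that the VAS score on postoperative day one may drop from a 4 to a 2" and "Assuming an SD of 1.6-1.8 for the purpose of estimations". A two-sample t-test for 2 points at 80% power needs 12 per arm at SD 1.6 and 14 per arm at SD 1.8, so 24 and 28 in total. This matches.

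Neither calculation uses covariates.

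**2. Inputs the documents do not give.** R² (the share of within-arm outcome variance explained by the factors), blood-thinner prevalence, procedure mix and prognostic strength are all assumed below and shown as ranges. As a guide for VAS, a 1-point gap between two equally common procedure groups gives R² = 0.25 × 1² / 1.8² = 7.7% at SD 1.8, or 9.8% at SD 1.6.

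**3. Precision.** Adjustment multiplies the standard error by √(1 − R²), which is equivalent to raising n to n/(1 − R²). At 118 per arm:

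| Assumed R² | SE ratio | n per arm for the same precision | Power, 30% v 15% | VAS difference detectable with 80% power (SD 1.8) |
|---|---|---|---|---|
| 0 | 1 | 118 | 79.2% | 0.66 |
| 5% | 0.975 | 118 × 0.95 = 112.1, so 113 | 81.2% | 0.64 |
| 10% | 0.949 | 118 × 0.90 = 106.2, so 107 | 83.3% | 0.62 |

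The power column uses the pooled-variance formula. It gives 79.2% at 118 where the plan's unpooled formula gives 80.1%, so gains should be read against 79.2%. For the planned 2 points on the VAS, power at 118 per arm is above 99.9% before any adjustment.

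**4. One binary factor and the recovery-unit outcome.** Assume prevalence of 5–50% and TXA halving risk in both strata.
- Factor raises risk 1.5-fold: R² 0.4–1.3%, power 79.3–79.7%.
- 2-fold: R² 1.4–4.1%, power 79.8–80.9%.
- 3-fold: R² 5.2–10.9%, power 81.3–83.6%.

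The gain is thus about 0 to 4 points. A simulation with both factors together (125 per arm, 50% procedure mix, 15% blood thinners, 2,000 runs) agrees. Unadjusted against adjusted power was 82.0 v 83.2% for odds ratios of 2, 83.1 v 85.1% for 3, and 82.6 v 86.0% for 4, so gains of 1.2, 2.0 and 3.4 points.

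**5. Chance imbalance.** The SD of the between-arm difference in a factor with prevalence q is √(2q(1 − q)/118). The 95% range is ±7.7 points at q = 10%, ±10.2 at 20% and ±12.8 at 50%. The probability of a gap of 10 points or more is 1.3%, 6.1% and 13.4%. Converted into a shift in the treatment estimate:
- VAS: 0.128 × 1 point = 0.13 points, about 6% of the planned 2.
- Recovery unit, 20% prevalence, 2-fold risk (control 25% v 50%, TXA 12.5% v 25%), with the 10.2-point gap split evenly between arms: 5.1 × 0.25 + 5.1 × 0.125 = 1.9 points, against a planned difference of 15.

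**6. The stand-alone subset.** With about 250 enrolled (125 per arm) and 10–20% users, the subset has 12.5 to 25 per arm. Power for 30% v 15% is Φ(0.15/√(0.3375/12.5) − 1.96) = 14.8%, rising to 25.2% at 25 per arm.

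**The case against.** **The plan does not commit to an unadjusted analysis.** A reader might infer that VAS, gauze use and the recovery-unit outcome will all be compared without covariates. The documents do not support that. The Z-test sentence describes a sample-size calculation for one secondary outcome, and no model is named for anything. Adjustment is unspecified, not ruled out. This stands, and it is why the gain is described as not secured.

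**Procedure type is not relegated to context.** A reader might extend the blood-thinner sentence to procedure type. It does not reach that far. Procedure type has no stated role and is not listed as a study variable, so the gap is wider there, and the fix needs one more recorded field.

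**The benefit is small and every driver of it is assumed.** This also stands. Under randomisation the unadjusted estimate is unbiased and its standard error already allows for imbalance, so it would be wrong to infer bias. Blood-thinner status at screening may also be a weak marker of exposure at surgery, because medication follows standard of care before and after the operation.

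**The subset is only contextual.** No confirmatory test within it is claimed, and low power is usual for such a subset. An interaction estimate will be imprecise too. What remains is that an interaction with a confidence interval shows that imprecision openly and addresses directly whether the effect differs.

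**Conclusion.** The point holds as a minor omission, with moderate confidence. Two factors available before randomisation are used neither in the allocation nor in a prespecified model, and the one stated use, for blood thinners only, is a subset. Under an assumed R² of 5–10%, adjustment would cut the standard error by about 2.5–5%. For recovery-unit evaluation, which drives enrolment, it would add about 0 to 4 points of power across the assumed strengths. For the VAS it would only narrow the interval slightly. Large imbalance is uncommon at the planned size.

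A reader might infer that the trial is underpowered or mis-sized because of this. It is not: both stated sample sizes reproduce from their own inputs, and neither depends on adjustment.

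**What to change.** In Sections 2.a and 2.g:

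- Prespecify that the main analyses adjust for blood-thinner use (yes/no, as recorded at screening) and scheduled procedure type (any endoscopic sinus surgery v septal or turbinate surgery only, with combined operations classed as endoscopic sinus surgery).
- List scheduled procedure type as a recorded study variable.
- Use linear or mixed-model regression for VAS and gauze use.
- For recovery-unit evaluation, use logistic regression reported as a standardised risk difference, so that the quantity estimated remains the difference in proportions on which the 118 per group is based.

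In Section 8.i, replace the stand-alone blood-thinner subset with a treatment-by-blood-thinner interaction estimate and 95% CI, labelled exploratory.

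The cost is protocol wording, one extra recorded field and slightly more analysis work. No extra patients are needed and no sample size changes.
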